7.10 Analyses of Columbia-Suicide Severity Rating Scale (C-SSRS)

The following summaries will be presented for C-SSRS scale in the safety analysis set:

- Descriptive statistics by study visit.
- Number of subjects with positive reports at baseline and during treatment.
- A shift-table to demonstrate changes from baseline in C-SSRS scores during treatment.

A subject with a positive report at baseline if the subject reported any of the following suicidal ideation or behavior:

- Active suicidal ideation with some intent to act, without specific plan.
- Active suicidal ideation with specific plan and intent.
- Any actual suicide attempt.
- Any interrupted suicide attempt.
- Any aborted suicide attempt.
- Any preparatory acts or behavior.

A subject with a positive report during treatment if the subject reported any of the following suicidal ideation or behavior:

- Active suicidal ideation with some intent to act, without specific plan.
- Active suicidal ideation with specific plan and intent.
- Any actual suicide attempt.
- Any interrupted suicide attempt.
- Any aborted suicide attempt.
- Any preparatory acts or behavior.
- Completed suicide.

7.11 Pharmacokinetic/Pharmacodynamic Analysis

Plasma concentrations of vortioxetine and paroxetine will be presented in the data listings.

A population PK analysis will only be conducted for vortioxetine and/or paroxetine if deemed.

7.12 Pharmacogenomic Analyses

A pharmacogenomic analysis plan will be prepared prior to the exploratory pharmacogenomic analysis. This plan will describe the underlying hypotheses, the pharmacogenomic analysis set, genes that will be included in the analysis and the statistical methods to be used.

7.13 Safety Analysis

Safety summaries will be based on the safety set. Conventions for the definition of baseline values and visit windowing are given in Section 7.1.3. Missing safety data will not be imputed. Safety summaries will include descriptive statistics for values, changes, and incidence of events for all treatment groups combined in addition to summary by treatment group.

7.13.1 Adverse Events

All adverse events will be coded using MedDRA version 19.0. In this dictionary, each verbatim term is coded to a lower level term, and then mapped to a preferred MedDRA term, which is then

mapped to an SOC. All adverse events will be included in the data listings but only treatment-emergent adverse events will be included in the summary tables.

A treatment-emergent adverse event (TEAE) is defined as an adverse event with an onset that occurs after receiving study drug (AE start date \geq first dose date) and within 30 days after receiving the last dose of study drug (AE start date – last dose date \leq 30). A TEAE may also be a pretreatment adverse event or a concurrent medical condition diagnosed prior to the date of first dose of study drug that increases in severity after the start of dosing. Adverse events data with onset occurring more than 30 days after last dose of study drug (AE start date – last dose date $>$ 30) will be listed, but not included in the summary tables. Adverse events with missing onset dates will be summarized regardless of severity and relationship to study medication.

Serious adverse events (SAEs) with onset that occurs after receiving study drug (AE start date \geq first dose date) and within 30 days after receiving the last dose of study drug (AE start date - last dose date \leq 30) will be summarized.

In the high-level adverse event summary tables, TEAEs will be summarized regardless of intensity and relationship to study drug. Within each subject, multiple reports of events that map to a common MedDRA term will be counted only once.

At the adverse event level, the summary tables will present the number of subjects reporting each of these MedDRA events, ie, the number of subjects reporting 1 or more events that map to the given MedDRA term.

At the SOC level, the summary tables will present the number of subjects reporting 1 or more events that map to the given SOC. That is, the number of subjects reported at the SOC level will be less than or equal to the sum of the subject counts across all adverse events within that SOC.

In selected summaries (TEAEs overview, and TEAEs by SOC and preferred term), adverse events will be summarized by the number of events reported in addition to the number and percentage of subjects with events.

For the summary of TEAEs by SOC, preferred term and maximum intensity, if a subject experiences more than 1 episode of a particular coded adverse event, the subject will be counted only once by the maximum intensity of the episode (preferred term). Similarly, if a subject has more than 1 adverse event within an SOC, the subject will be counted only once by the maximum intensity in that SOC. Adverse events with missing severity will be classified as having the highest severity.

TEAEs classified in the eCRF as possibly or probably related to the study medication will also be summarized by preferred term and SOC. If a subject experiences more than 1 episode of a particular coded adverse event, the subject will be counted only once by the most related report for the preferred term. Similarly, if a subject has more than 1 adverse event within an SOC, the subject will be counted only once by the most related report in that SOC. Adverse events with missing relationship will be classified as having the highest relationship to study drug.

The following summaries will be presented:

- Overview of TEAEs during the study - number and percentage of subjects, number of events.

CONFIDENTIAL

- Pretreatment adverse events by SOC and preferred term.
- TEAEs by SOC and preferred term - number and percentage of subjects, number of events.
- TEAEs by SOC and preferred term by sex (male and female) - number and percentage of subjects, number of events.
- TEAEs by SOC and preferred term by age group (\leq median, $>$ median) - number and percentage of subjects, number of events.
- TEAEs by SOC - number and percentage of subjects.
- TEAEs by preferred term - number and percentage of subjects.
- Intensity of TEAEs by SOC and preferred term - number and percentage of subjects.
- Drug-related TEAEs by SOC and preferred term - number and percentage of subjects, number of events.
- Intensity of Drug-related TEAEs by SOC and preferred term - number and percentage of subjects.
- TEAEs leading to study discontinuation by SOC and preferred term - number and percentage of subjects, number of events.
- Treatment-emergent SAEs by SOC and preferred term - number and percentage of subjects, number of events.

SOCs will be sorted by alphabetical order. Within an SOC, adverse events will be sorted in descending order of total number of subjects with the preferred term among all the treatment groups.

All adverse events will be listed by treatment, study center, subject number and onset date of the adverse event. The listing will contain: subject identifier, age, sex, body weight, race, adverse event (preferred term and reported term), SOC, onset date, end date or whether the event was ongoing, duration, frequency, intensity (mild, moderate or severe), action taken concerning study drug (change in concomitant medication, change in IMP, or subject withdrawal), causality to study drug (not related or related), the outcome (recovered, recovering, not recovered, recovered with sequelae, unknown, or fatal), whether the adverse event was an SAE.

Special listings for TEAEs leading to study discontinuation, SAEs, deaths, and if needed, AE of special interest will also be presented.

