6.0 STUDY DESIGN AND DESCRIPTION

6.1 Study Design

This is a phase 4, multicenter, randomized, double-blind, placebo- and active-controlled (paroxetine), 4-arm, parallel group, fixed-dose study comparing the effect of vortioxetine (10 and 20 mg QD) vs paroxetine (20 mg QD) on sexual functioning after 5 weeks of treatment in healthy adult men and women. This outpatient study will be conducted at approximately 15 sites in North America. Men and women will be enrolled in approximately equal proportions (ie, 50% men and 50% women, overall). Enrollment will be capped for each sex when the enrollment target has been met for that sex stratum.

[figure not shown]
After providing informed consent, subjects will be assessed for study eligibility during a Screening Period of up to 4 weeks. Healthy subjects who have normal sexual functioning (as defined by the CSFQ-14), have been in a steady relationship for ≥ 3 months, are currently sexually active, and meet all other study entry criteria will be enrolled. At Baseline (Day 0), eligible subjects will be equally (1:1:1:1) randomized to double-blind vortioxetine 10 mg, vortioxetine 20 mg, paroxetine 20 mg, or placebo and will be treated for 5 weeks. Randomization will be stratified by sex.

Subjects allocated to vortioxetine 20 mg will initiate treatment at 10 mg/day for the first week. Subsequently, the dose will be increased to 20 mg/day and remain at 20 mg/day until study completion. Subjects allocated to vortioxetine 10 mg will initiate treatment at 10 mg/day and remain at 10 mg/day until study completion. Subjects allocated to paroxetine 20 mg will initiate treatment at 20 mg/day and remain at 20 mg/day until study completion. Subjects will be instructed to take their first dose of study drug the day after Baseline on Day 1, preferably in the morning. After randomization, subjects will be seen for weekly visits and receive a follow-up safety contact 2 weeks after the end of double-blind treatment. At the end of 5 weeks of treatment, or at Early Termination (ET), all subjects will abruptly discontinue study drug.

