10.2 Procedures

10.2.1 Collection and Reporting of AEs

Collection of PTEs will commence from the time the subject signs the informed consent to participate in the study and continue until the subject is first administered study drug (on Day 1) or until screen failure. For subjects who discontinue prior to study drug administration, PTEs are collected until the subject discontinues study participation.

Collection of AEs will commence from the time that the subject is first administered study drug (on Day 1). Routine collection of AEs will continue until the Follow-up Contact (Week 7).

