13.1.6 Safety Analysis

AEs

AEs will be reported throughout the study. AEs will be summarized using the safety analysis set.

The definition of treatment-emergent AEs will be provided in the statistical analysis plan. AEs will be coded using MedDRA and will be summarized by system organ class and preferred term for the double-blind Treatment Period and the entire study.

AEs that were reported more than once by a subject during the double-blind Treatment Period will be counted only once for that subject at the maximum severity.

Clinical Evaluations

Absolute values and changes from Screening/Baseline for clinical laboratory tests, vital signs, and weight will be summarized for each treatment group using descriptive statistics. Clinical laboratory test and vital sign results that are outside the normal ranges and potentially clinically significant will be flagged and tabulated. Physical examination findings will also be summarized for each treatment group.

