Appendix A Schedule of Study Procedures

Study Day/Week:	Screening Period	Base-line	Double-Blind Treatment Period				Final Visit/ET Visit (a)	Follow-up Contact (b)
	Days -28 to -1	Day 0	Week 1	Week 2	Week 3	Week 4	Week 5	Week 7
Visit Windows (Days Relative to Baseline [Day 0]):		0	±3	±3	±3	±3	±3	±5
Visit Number:	1	2	3	4	5	6	7	
Screening/Baseline Procedures								
Informed consent	X							
Subject registry database	X							
Demographics, medical and/or psychiatric history, medication history	X							
Height, BMI	X							
ECG	X							
HBsAg, HCV, HIV, free testosterone, TSH, free T4, HbA1c (c)	X							
Urine drug screen	X	X						
Concurrent medical and psychiatric conditions	X	X (d)						
Inclusion/exclusion criteria	X	X (d)						
Eligibility verification	X	X (e)						
Safety Assessments								
Physical examination, weight	X	X					X	
Vital signs	X	X		X			X	
Concomitant medications	X	X	X	X	X	X	X	X
Hematology, serum chemistry, urinalysis	X	X (f)					X (f)	
C-SSRS	X	X	X	X	X	X	X	
PTE assessment (g)	X	X						
AE assessments (h)			X	X	X	X	X	X
Pregnancy test (hCG) (i)	X	X	X	X	X	X	X	
Sexual Functioning Assessments								
CSFQ-14 (j)	X	X	X	X	X	X	X	
PGI-I (j)			X	X	X	X	X	
Other Blood Sampling								
PK sample collection (k)					X	X	X	
DNA PGx sample collection (l)		X						
RNA PGx sample collection (m)		X					X	
Clinical Supplies								
Contact IWRS for subject ID/medication ID/subject status	X	X	X	X	X	X	X	

CONFIDENTIAL

Study Day/Week:	Screening Period	Base-line	Double-Blind Treatment Period					Final Visit/ET Visit (a)	Follow-up Contact (b)
	Days -28 to -1	Day 0	Week 1	Week 2	Week 3	Week 4	Week 5	Week 7	
Study drug compliance technology		X	X	X	X	X	X		
Dispense study drug		X (n)	X	X	X	X			
Study drug return/accountability/compliance			X	X	X	X	X		

(a) Final Visit procedures to be conducted for subjects who withdraw early, except for those who withdraw their consent and refuse further contact.

(b) The Follow-up Contact will be conducted by telephone.

(c) TSH to be measured at Screening to exclude subjects with clinically significant thyroid dysfunction (hyperthyroidism or hypothyroidism), which may impact sexual functioning. If TSH value is outside the normal range, free T4 will be measured.

(d) To be updated at Baseline.

(e) A prerandomization form must be approved by the PPD medical monitor prior to randomization.

(f) Blood samples for clinical laboratory tests to be collected under fasting conditions at Baseline and Week 5/ET.

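### SAP 7.13.1 omits the on-treatment adverse event summary that the protocol requires, and selects drug-related events by causality grades the trial does not record

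*SAP*

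**What the plan says.** **Protocol.** Section 13.1.6, and the safety paragraph of the Study Summary in the same terms, says that adverse events will be "summarized by system organ class and preferred term for the double-blind Treatment Period and the entire study". Its counting rule is tied to the first of those periods: events "reported more than once by a subject during the double-blind Treatment Period will be counted only once for that subject at the maximum severity". One matter is delegated: "The definition of treatment-emergent AEs will be provided in the statistical analysis plan". Section 6.1 states how treatment ends: "At the end of 5 weeks of treatment, or at Early Termination (ET), all subjects will abruptly discontinue study drug". Section 10.2.1 continues routine event collection to the Week 7 contact. Sections 10.1.7 and 10.2.1.1 record causality to study drug in two categories, Related and Not Related.

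**SAP.** Section 7.13.1 puts only treatment-emergent events in its treatment-period and later summaries. It defines these as events with onset on or after the first dose "and within 30 days after receiving the last dose of study drug", plus earlier conditions that worsen after dosing starts. It then lists 12 summaries: one of pretreatment events and 11 of treatment-emergent events. For drug-related events it says: "TEAEs classified in the eCRF as possibly or probably related to the study medication will also be summarized". Events with missing causality are set to the highest relationship. The adverse event listing described later in the same section shows causality as not related or related. Section 7.15 declares no changes.

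**The concern.** The safety objective is to compare vortioxetine and paroxetine with placebo. Events while taking a drug and events after stopping it abruptly are different things, and the protocol plans to show the on-drug period separately. Under the SAP no table does so, for incidence or for maximum intensity. A subject with a mild event on drug and a severe episode of the same preferred term after stopping would be counted once, as severe, with nothing to show that the severe episode came after the last dose. If arms differ in what happens after stopping, that difference appears in the treatment-emergent tables mixed with any on-drug difference.

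The causality filter is a separate defect in the same section. A table that selects on categories the trial does not record cannot show what its title says.

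**Working it through.** **1. Periods required and periods planned**

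| | Treatment Period only | Whole study |
|---|---|---|
| Protocol 13.1.6 and Study Summary | required, by system organ class and preferred term | required, by system organ class and preferred term |
| SAP 7.13.1, 11 treatment-emergent summaries | 0 of 11 | 11 of 11 (first dose to 30 days after last dose) |

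The protocol hands the definition of treatment-emergent to the SAP. It does not hand over the choice of reporting periods, which the same section fixes.

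**2. Could the 30-day tables serve as the Treatment Period tables?**

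Inputs are the visit windows in Appendix A of the protocol, in days relative to Baseline (Day 0).

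- Final visit: Week 5 = Day 35 ± 3, so Day 32 to 38.
- Follow-up contact: Week 7 = Day 49 ± 5, so Day 44 to 54.
- Shortest gap: 44 − 38 = 6 days. Longest gap: 54 − 32 = 22 days. Nominal gap: 49 − 35 = 14 days.

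This assumes the last dose falls on the day of the final visit. If it was the day before, the gap is 7 to 23 days. Either way it is below 30, so for subjects stopping at Week 5 the window takes in every routinely collected event after stopping. For them the tables are whole-study tables. The nominal off-drug share of calendar time is 14/49 = 29%; this is a share of days, not of events.

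Early terminators depend on when their contact takes place. If it is 2 weeks after stopping, the same conclusion follows. If it stays at Week 7 from Baseline, events beyond 30 days become possible for a stop before Day 49 − 30 = 19 (before Day 54 − 30 = 24 at the window edge). No claim is made for this group.

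**3. How large could the mixing be?**

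The documents give no event rates, so this is an illustration under assumptions. Let two arms have the same on-drug incidence p. Among subjects with no on-drug event, let the incidence of a first event after stopping differ between the arms by d. The pooled table then shows a difference of (1 − p) × d although there is no on-drug difference.

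| Assumed p | Assumed d | (1 − p) × d | Of 88 subjects per arm |
|---|---|---|---|
| any | 0 | 0 | 0 |
| 60% | 5 points | 0.40 × 0.05 = 2 points | 1.8 |
| 40% | 10 points | 0.60 × 0.10 = 6 points | 5.3 |
| 20% | 15 points | 0.80 × 0.15 = 12 points | 10.6 |

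Over p from 20% to 60% and d from 0 to 15 points, the range is 0 to 12 points. These values of p suit the any-event line of the overview table better than single preferred terms, where incidence would usually be lower.

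**4. Causality categories**

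| Place | Categories |
|---|---|
| Protocol 10.1.7 (definitions) | Related, Not Related |
| Protocol 10.2.1.1 (item documented in the eCRF) | related, not related |
| SAP 7.13.1, adverse event listing | not related, related |
| SAP 7.13.1, selection for drug-related summaries | possible, probable |

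Only the last row uses grades. Two of the 12 summaries depend on it: drug-related events by system organ class and preferred term, and their intensity. Applied literally to a two-category field, the filter selects no event with a recorded causality. The only events left are those with missing causality, which the SAP sets to the highest relationship.

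**The case against.** The case for leaving the plan alone has four parts.

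- **The definition is delegated.** The protocol lets the SAP define treatment-emergent, and a 30-day window is permissible. This is right, and the window is not criticised here. It does not supply the second reporting period.
- **The loss is modest.** The adverse event summaries are descriptive. Onset and last-dose dates are both listed, so the split can be made later. This stands as a limit on the consequence. But a split made after unblinding is no longer pre-specified, and the protocol had specified it.
- **One table comes close.** Events leading to discontinuation will mostly have started on drug. True in practice, but that table does not give overall on-drug incidence or intensity.
- **The causality wording is a drafting slip.** The tables are titled drug-related, and a programmer with a two-category field would probably select Related. The eCRF itself is not among the documents, so its categories are inferred from the passages compared above. That makes this part easy to repair, but the wording remains wrong, and an approved analysis plan should not depend on being read against its text.

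The illustrative range in the working rests on assumed inputs and includes zero. It shows what could happen and is not evidence that distortion will occur.

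**Conclusion.** Both points hold. The SAP drops a summary that the protocol requires in two places, without declaring a change, and its 30-day tables cannot replace it for subjects stopping at Week 5. That conclusion assumes a last dose on or about the day of the final visit and a follow-up contact within its window. The causality filter matches no category described elsewhere in either document, so as written it gives a wrong result in two tables.

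The effect on reported incidence cannot be sized from the documents. The consequence is confined to safety reporting; the primary and other efficacy analyses are untouched. The SAP should be corrected, but this does not threaten the trial's main conclusion.

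**What to change.** In SAP 7.13.1:

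1. Add the protocol's Treatment Period summaries for the overview, the system organ class and preferred term table, and the maximum-intensity table. Onset from first dose through last dose is a workable definition. The protocol does not say how to assign an event that starts just after the last dose, so the SAP should state the cut-off explicitly.
2. Keep the existing tables, first dose to 30 days after last dose, and label them as the whole-study summary. A separate post-treatment table is optional.
3. Replace the graded causality wording with Related, after checking the causality field in the eCRF. Keep the rule for missing causality.

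The cost is SAP wording, a few extra tables from dates already collected, and one corrected filter. No new data are needed.

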7.13.2 Clinical Laboratory Evaluations

The following clinical laboratory parameters will be summarized:

- Serum chemistry including blood urea nitrogen (BUN), sodium, alkaline phosphatase, potassium, calcium, creatinine, glucose, γ -Glutamyl transferase, alanine aminotransferase (ALT), aspartate aminotransferase (AST), total bilirubin, albumin, creatine kinase, and total protein.

- Lipids including cholesterol total, triglycerides, high-density lipoprotein (HDL), and low-density lipoprotein (LDL).
- Hematology including white blood cell count (WBC), red blood cell count (RBC), hemoglobin, hematocrit, platelets, neutrophils, eosinophils, basophils, lymphocytes, and monocytes.
- Urinalysis including specific gravity, pH, protein, glucose, and occult blood.

For each laboratory parameter, the following will be displayed for each scheduled time point (each visit and end of study).

- Summary statistics (n, mean, SD, median, minimum, and maximum) by treatment group and overall for the actual values and change from Baseline values.
- Shift tables for the change from Baseline to each post-baseline time point will be presented. For these tables each subject will be categorized as low, normal, or high for the baseline value, and low, normal, or high for each post-Baseline time point, according to the central laboratory reference ranges. The number of subjects in each of the combinations of shifts will be presented.

Potentially clinically significant (PCS) laboratory values, as defined in [A Randomized, Double-Blind, Parallel Group, Placebo- and Active-Controlled, Phase 4 Study Evaluating the Effect of Vortioxetine 10 and 20 mg/day vs Paroxetine 20 mg/day on Sexual Functioning in Healthy Subjects. Takeda Development Center Americas, Inc ., Protocol No. Vortioxetine-4001 Incorporating Amendment No. 01, dated 10 January 2017](#), will be summarized by treatment group and overall. The number and percentage of subjects with PCS values observed post-Baseline in each of the applicable laboratory parameters will be presented.

A listing of all laboratory data will be provided. Laboratory data outside of the normal reference range will be flagged on the listing along with values meeting PCS criteria. The listing will also include the age (at consent) and sex of the subject. Listings of PCS laboratory values will also be presented. Thyroid stimulating hormone, Free T₄ (c), and direct bilirubin will not be summarized but will be listed.

When lab values are recorded in the form of “ $<x$ ” or “ $>y$ ”, “ x ” will be used for “ $<x$ ” and “ y ” will be used for “ $>y$ ” in the PCS summary tables. However, these values will be displayed as is when the individual subject data listings are presented.

Summaries and listings of laboratory data will be presented, as appropriate, in Systeme International (SI) and conventional units.

